### Secondary objectives:

2. Evaluate acute (0 to 24 hours), delayed (>24 to 120 hours), and overall (0-120 hours) CINV indicators in each cycle of chemotherapy

Time 0 is defined as the start time of the chemotherapy administration on Day 1 of each of the three cycles. CINV indicators are nausea and vomiting, their intensity and frequency and Quality of Life in the acute, delayed and overall period.

CONFIDENTIAL

Confidential	MyRisk	Date: 05 February 2024
	Protocol	
	PROTOCOL NUMBER: IBA1160	Version: 5.1

3. Evaluate the predictive role of potential risk factors in the development of CINV over three cycles of chemotherapy

Potential risk factors for CINV are those thought to be increasing the risk of CINV in patients receiving MEC as reported in section 3.3.3. Risk factors for CINV and in section 3.6.3.1 where the risk score algorithm calculation by using predictive factors for CINV is explained.

4. Evaluate the safety profile of the antiemetic drug over three cycles of chemotherapy

5. Explore the effect of CINV on daily activities and quality of life in patients receiving moderately-emetogenic chemotherapy over three cycles of chemotherapy

6. Evaluate resource utilization and health economic outcome

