4.2. Secondary Objectives

The secondary objectives are:

- To evaluate acute (0 to 24 hours), delayed (>24 to 120 hours), and overall (0 to 120 hours) CINV indicators in each cycle of chemotherapy
- To evaluate the predictive role of potential risk factors in the development of CINV over three cycles of chemotherapy
- To evaluate the safety profile of the antiemetic drug over three cycles of chemotherapy
- To explore the effect of CINV on daily activities and quality of life in patients receiving moderately-emetogenic chemotherapy over three cycles of chemotherapy
- To evaluate resource utilization and health economic outcome

Time 0 is defined as the start time of the chemotherapy administration on Day 1 of each of the three cycles. CINV indicators are nausea and vomiting, their intensity and frequency and Quality of Life in the acute, delayed and overall period.

Information on CINV indicators during acute and delayed phase will be taken from MAT questionnaires. Daily information (apart from Day 1) will be taken from Patient's Diary.

Potential risk factors for CINV thought to be increasing the risk of CINV in patients receiving MEC are reported in section 3.3.3 of the study protocol. Risk factors for CINV are described also in section 3.6.3.1 of the study protocol where risk score algorithm calculation by using predictive factors for CINV is explained.

5. Study Design

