6.2. Secondary Endpoints

Clinical secondary endpoints will be evaluated during each cycle:

- Complete response during the acute (0-24h), delayed phase (>24-120h), overall (0-120h) and daily in each cycle
- No emetic episode during the acute, delayed and overall phase and daily in each cycle
- Number of vomiting episodes during the acute, delayed and overall phase in each cycle
- No rescue medication during the acute, delayed and overall phase and daily in each cycle
- No significant nausea (maximum MAT scale = 2) during the acute, delayed and overall phase and daily in each cycle;
- No nausea (MAT scale = 0) during the acute, delayed and overall phase and daily in each cycle;
- Complete protection (no emetic episode, no rescue medication and no significant nausea) during the acute, delayed and overall phase and daily in each cycle
- Nausea and Vomiting-related quality of life indicators (through the Functional Living Index Emesis scale)
- Collection of chemotherapy delays and/or dose reductions (Delay of chemotherapy administration due to CINV will be also evaluated as part of health economic endpoints)

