7.8. Unscheduled/Repeated Assessments

In this study, the patients are followed for three consecutive cycles of chemotherapy. That is why the endpoint and secondary analysis will take into account a correlation between observations from one patient.

Unscheduled assessment should not occur and are not included in the CRF.

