9.4.1. Imputation of endpoints data

To achieve the largest possible sample, imputation techniques will be used to impute missing data for the FAS population. Missing data on the primary efficacy endpoint will be imputed using conventional Multiple Imputations approach. The SAS® MI procedure will be employed to perform multiple imputation in order to obtain Maximum Likelihood estimates which, by definition, are unbiased under a MCAR and MAR mechanism for missing values.

The following MI procedure code will be used to perform MI with 5 imputations.

```
PROC MI data = dataset seed=s out = MIdataset n impute = 5;
VAR study_treatment carboplatin country vis1_event - vis3_event;
CLASS study_treatment carboplatin country vis1_event - vis3_event;
monotone logistic;
RUN;
```

The exact names of the variables may differ.

9.4.2. Missing data within the FAS population on secondary efficacy endpoints will be imputed using the last observation carried forward (LOCF). Primary Efficacy Endpoint

The primary efficacy endpoint “Proportion of complete responses over three cycles of chemotherapy after the start of the MEC administration” will be analyzed by means of a generalized linear model (GLIM) with logit link function, binomial distribution and with “study treatment” (NEPA + Dex or Standard of care), “carboplatin use” (yes or no) and “country” as factors, using data from the overall period of three cycles.

Moreover, the GLIM model will be parameterized with generalized estimating equations with an exchangeable working correlation matrix to take into account clustered data (i.e. three repeated measures corresponding to as many cycles of chemotherapy within each subject). Results will be reported as odds ratios with associated two-sided 95% confidence intervals and p-values.

The results will be obtained via the GENMOD procedure, using following code:

```
PROC GENMOD data = dataset;
CLASS id study_treatment carboplatin country;
MODEL complete_response = study_treatment carboplatin country / dist = bin
link = logit;
REPEATED subject = id / type = exch covb corrw;
LSMEANS study_treatment / diff exp ilink cl;
RUN;
```

The exact names of the variables may differ.

With MI the code will be modified to:

```
PROC GENMOD data = dataset;
CLASS id study_treatment carboplatin country;
MODEL complete_response = study_treatment carboplatin country / dist = bin
link = logit;
REPEATED subject = id / type = exch ecovb;
LSMEANS study_treatment / diff exp ilink cl;

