9.4.3. Secondary Efficacy Endpoint

The same statistical approach as for the primary endpoint (GLIM) will be used for all the secondary efficacy endpoints with the exception of the following outcomes “delay and/or dose reduction” which will be analyzed using a Stratified Wilcoxon Rank Sum test blocking for carboplatin use and country, using following code (*delay_length* can be replaced with *amount_reduction*):

```

PROC NPAR1WAY data=dataset wilcoxon;
CLASS study_treatment;
VAR delay_length;
STRATA country carboplatin;
EXACT wilcoxon;
RUN;

```

The exact names of the variables may differ.

The code will be equivalent to the one used in the analysis of primary endpoint, only changing variable from *complete_response* to variables describing the secondary endpoints:

- Complete response during the acute (0-24h), delayed phase (25-120h), overall (0-120h) and daily in each cycle
- No emetic episode during the acute, delayed and overall phase and daily in each cycle
- Number of vomiting episodes during the acute, delayed and overall phase in each cycle
- No rescue medication during the acute, delayed and overall phase and daily in each cycle
- No significant nausea (maximum MAT scale = 2) during the acute, delayed and overall phase and daily in each cycle
- No nausea (MAT scale = 0) during the acute, delayed and overall phase and daily in each cycle
- Complete protection (no emetic episode, no rescue medication and no significant nausea) during the acute, delayed and overall phase and daily in each cycle
- Nausea and Vomiting-related quality of life indicators (through the Functional Living Index Emesis scale)

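### Phase and daily secondary endpoints are defined in each cycle, but the secondary-endpoint code has no cycle term, so no by-cycle treatment comparison is clearly prespecified

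*SAP*

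**What the plan says.** The unit of evaluation is the cycle. The second objective in the protocol (sections 1 and 2.2) concerns "CINV indicators in each cycle of chemotherapy", and SAP 4.2 repeats it: "To evaluate acute (0 to 24 hours), delayed (>24 to 120 hours), and overall (0 to 120 hours) CINV indicators in each cycle of chemotherapy". SAP 6.2 introduces its list with "Clinical secondary endpoints will be evaluated during each cycle".

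SAP 9.4.3 sets the analysis. Apart from chemotherapy delay and dose reduction, which get a stratified Wilcoxon test, it says: "The code will be equivalent to the one used in the analysis of primary endpoint, only changing variable". The variables listed after that sentence keep the per-cycle wording, for example "overall (0-120h) and daily in each cycle".

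The program being reused is printed in SAP 9.4.2. Its class variables are "CLASS id study_treatment carboplatin country" and its model line is "MODEL complete_response = study_treatment carboplatin country / dist = bin". It has a REPEATED statement on patient with exchangeable correlation and one LSMEANS request, on treatment. The accompanying text describes the data as three repeated measures per patient, one per cycle. Protocol section 8.4 prescribes the same approach for the secondary endpoints and adds nothing about cycle. SAP 9.4.1 and 9.4.2 assign multiple imputation to the primary endpoint and LOCF to the secondary ones.

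**The concern.** The endpoints ask for a result per cycle, and the only program given for the binary ones pools the cycles. A reader of the final report could then see a single odds ratio for, say, no significant nausea in the delayed phase, with no treatment estimate or interval for any one cycle.

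The protocol itself treats cycle as important to the outcome. Sections 1 and 2 say that risk is highest in cycles 1 and 2 and then declines, and the score in section 3.6.3.1 subtracts 5 points before the second cycle and 6 from the third onward. That concerns the underlying risk of CINV, not a changing treatment effect. It does explain why results were wanted by cycle.

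There is also a practical risk. SAP 9.1.5 requires double programming of the secondary efficacy analyses. Two competent programmers could read 9.4.3 differently, one fitting a pooled model and the other three separate ones.

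**Working it through.** **1. What the program returns.** The statements in SAP 9.4.2 are CLASS (patient, treatment, carboplatin, country), MODEL (treatment, carboplatin, country), REPEATED (patient, exchangeable) and LSMEANS (treatment). There is no cycle variable, treatment-by-cycle term, BY or WHERE. The multiple-imputation version of the model has no cycle term either. With three records per patient there is one treatment coefficient, hence one odds ratio per endpoint and window. If the response is overall (0-120 h) complete response, outcome and model are those of the primary analysis and only the imputation differs.

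**2. The plan's own figure.** Inputs from SAP 9.2: 71% versus 60%, two-sided 0.05, 80% power, three cycles, correlation 0.5, missing 0%, 7.5% and 15% combined independently.
- Observed fractions 1, 0.925 and 0.85 sum to 2.775.
- Variance factor with independence weights: v = [2.775 + 2 × 0.5 × (0.925 + 0.85 + 0.78625)] / 2.775² = 5.33625 / 7.700625 = 0.693.
- V = 1/(0.71 × 0.29) + 1/(0.60 × 0.40) = 9.023; log odds ratio d = ln 1.632 = 0.490.
- n per arm = (1.960 + 0.842)² × V × v / d² ≈ 204.5, so 205 per arm and 410 in total.

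The stated 410 reproduces. It is sized for the pooled comparison.

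**3. What pooling hides (assumed rates).** The documents give no rates by cycle, so these patterns are illustrations. Control is 60% in every cycle, odds 1.5.
- NEPA 77%: (0.77/0.23)/1.5 = 2.23
- NEPA 71%: (0.71/0.29)/1.5 = 1.63
- NEPA 65%: (0.65/0.35)/1.5 = 1.24

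With complete data and exchangeable correlation every record has equal weight, so the NEPA arm is fitted at (77 + 71 + 65)/3 = 71% and the pooled odds ratio is 1.63.

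GEE fits to 40,000 simulated patients per pattern (complete data, treatment as the only covariate in the pooled model) agree:

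| NEPA rate, cycles 1/2/3 | Pooled odds ratio | By-cycle odds ratios |
|---|---|---|
| 71/71/71% | 1.64 | 1.68, 1.61, 1.62 |
| 77/71/65% | 1.64 | 2.25, 1.63, 1.25 |
| 65/71/77% | 1.65 | 1.26, 1.63, 2.28 |

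The pooled model does not separate the three patterns.

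**4. Precision of a single cycle.** At the planning rates, power = Φ{[0.11√n − 1.96√(2 × 0.655 × 0.345)] / √(0.71 × 0.29 + 0.60 × 0.40)}, where n is the number per arm.
- Cycle 1, n = 205: 65%
- Cycle 2, n = 205 × 0.925 ≈ 190: 62%
- Cycle 3, n = 205 × 0.85 ≈ 174: 58%

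A single cycle would need 292 per arm for 80% power.

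**The case against.** The strongest reply is that the substituted variables are themselves listed in each cycle. Changing the variable could then mean one fit per cycle-specific variable, and that would give by-cycle odds ratios. This reading is possible. It also avoids the oddity of refitting the primary outcome. But the SAP does not state it, and with one record per patient the REPEATED statement would have no within-patient correlation to estimate. That makes the statement redundant, not invalid.

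A reader might go further and say that SAP 7.8 rules out per-cycle fits, because "the endpoint and secondary analysis will take into account a correlation between observations from one patient". The documents do not settle this: Secondary Analysis is also the title of SAP 9.8, the risk-factor analysis, and 7.8 may mean that.

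A reader might also infer that the second objective goes unanswered, or that persistence of the NEPA benefit is a named objective. Neither is supported. The objective asks for indicators to be evaluated in each cycle and names neither an arm comparison nor persistence. By-cycle frequencies might satisfy it. The titles of outputs 14.2-2 to 14.2-8 omit cycle, but SAP section 10 calls the list preliminary and the layouts are in Appendix 1, which was not available.

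Finally, the secondary endpoints are declared supportive only, and nothing in the documents suggests a waning effect. Both points stand. They limit the weight of the concern but do not remove it.

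**Conclusion.** The concern holds in this form: for the binary phase and daily endpoints defined in each cycle, no by-cycle treatment comparison is clearly prespecified, and the printed program, run on the data that the SAP describes, gives only a pooled three-cycle odds ratio.

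Under the assumed 77/71/65% pattern, by-cycle odds ratios from 2.23 down to 1.24 would be reported as about 1.63 to 1.64, the value for a constant 71%. That size rests wholly on the assumed rates; the absence of a cycle term does not.

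It does not follow that by-cycle results will be missing from the report. Delay and dose reduction are outside the point because they have their own test. So are the vomiting counts and FLIE scores, which are not binary; their fit to a binomial logit model is a separate question. The primary analysis and the sample size are unaffected.

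**What to change.** In SAP 9.4.3, for each binary endpoint and window:
- Add cycle and study_treatment*cycle to the CLASS and MODEL statements as appropriate, keeping carboplatin, country and the REPEATED statement.
- Report the three within-cycle odds ratios with 95% confidence intervals, from LSMEANS on study_treatment*cycle restricted to differences within cycle. Separate fits by cycle are an acceptable alternative if the SAP says so explicitly.
- Keep the pooled odds ratio as a summary.
- State how LOCF values enter the cycle 2 and cycle 3 estimates.
- Label the by-cycle results supportive, given the power in step 4.

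Add by cycle to the titles of the corresponding outputs among 14.2-2 to 14.2-8, and check the Appendix 1 shells against them.

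The cost is some SAP wording and a few lines of code before database lock. By-cycle intervals will be wider than pooled ones. Data collection does not change.

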9.5. Analysis of Safety

All the safety analyses will be performed on the Safety Set.

9.5.1. Adverse Events

Detailed definitions and classification of AEs are specified in Study Protocol, Section 10.

All Adverse Events (AEs) occurring after signing the informed consent through the AE reporting period are to be recorded on the AE pages of the eCRF irrespective of its relatedness to the study drug. The rules for recording AEs and their follow-up are described in Study protocol, Section 10.3.

Serious Adverse Events either related and not related to Akyntzeo® will be collected and communicated as per law requirements. A patient with multiple occurrences of a given AE will be counted only once in the AE category.

A reconciliation of serious adverse events (i.e. a comparison of the number of SAEs in the clinical database and the number of SAEs reported to sponsor) will be performed before DB lock. Assignment of treatment period and/or study period to AEs and coding should be done and approved by the sponsor before DB lock, as well.

All AEs will be summarized by their:

- Severity
- Seriousness
- Relationship to a drug

The number (%) of subjects reporting each treatment emergent AE (TEAE) will also be summarized by:

- Primary System Organ Class (SOC)
- Preferred Term (PT)

Subjects with more than one TEAE within a particular SOC and PT are counted only once for that SOC and PT. Percentages are based on the number of subjects actually receiving a given treatment (based on the safety population) within each treatment group.

An overall summary of AEs will be presented, including the frequency and percentage of patients with:

- Any treatment-emergent adverse event
- Any treatment-emergent adverse event related to a study drug
- Any treatment-emergent adverse event leading to chemotherapy dose reductions or interruptions
- Discontinuations Due to Adverse Event
- Any treatment-emergent serious adverse event
- On treatment deaths due to adverse event

In addition, following listings will be presented:

- All AEs (including pre-treatment AEs)
- Serious adverse events
- Adverse events resulting in withdrawn of study drug

No formal statistical tests will be performed.

9.6. Health Economic Analysis

The analytical approach will be a cost-efficacy analysis. This approach combines measures of costs over time with efficacy measures. The analyses will be performed on the Full Analysis Set.

9.6.1. Resource Utilisation

The analysis of medical consumption will be performed by comparing the amount of resources consumed per treatment group. Health care resource consumption will be expressed in units for each selected resource:

- Number of days and daily doses of rescue medication administered for the treatment of CINV
- Number of days of unplanned hospitalisation due to CINV
- Department of hospitalization
- Number of physicians' consultations due to CINV
- Number of re-hydration bags for at least grade 2 vomiting
- Number of unplanned laboratory tests
- Discontinuation from chemotherapy due to CINV
- Delay of chemotherapy administration due to CINV
- Days of absence from work

For each selected resource unit, both the frequency of use (i.e., % patient usage) and intensity of use (i.e., average amount used) will be presented.

Pooling of resource utilisation patterns will be undertaken unless any country effect or country x treatment interaction effect has been noted in the primary efficacy criteria.

9.6.2. Cost Estimates

The resource consumption will be valued by country, using average national charges / costs collected outside the clinical study by resource items; detailed valuation methods will be country-specific. The cost data will be collected outside of the study and then provided for analysis.

9.6.3. Cost-efficacy Analysis

The economic data will be collected primarily in physical units of health care resource used per patient and per event (efficacy / safety).

The incremental cost-efficacy ratio (ICER) is defined as the difference in cost between the study arms, divided by the difference in efficacy. It will be calculated in case a difference in efficacy is found between groups and if the costs in the Akynzeo group are higher. If that is not the case, then incremental costs (or savings) results across groups will be presented as cost-minimisation or cost-consequence results.

9.7. Interim Analysis

No interim analysis is planned for this study.

9.8. Secondary Analysis

An analysis with development of CINV as a dependent variable will be performed to identify additional potential risk factors of CINV. The analysis will be performed using the Per Protocol population. Data on 16 risk factors will be collected before each chemotherapy cycle:

1. Nausea and/or vomiting in the prior cycle of chemotherapy
2. Use of non-prescribed antiemetics at home in the prior cycle of chemotherapy
3. Platinum or anthracycline-based chemotherapy
4. Age < 60 years
5. Expectation for (anticipating) nausea and/or vomiting
6. History of morning sickness during previous pregnancy
7. Cycle of chemotherapy
8. <7 h of sleep the night before chemotherapy (to be obtained at day of chemotherapy)
9. History of any nausea and vomiting such as motion sickness, vestibular dysfunction...
10. Anticipatory nausea and/or vomiting
11. Anxiety over the past 24hrs (to be obtained at day of chemotherapy)
12. Alcohol intake (number of units per week)
13. Gender
14. Fatigue experience (symptom)
15. Smoking status
16. Weight

The first 7 factors are used throughout this study to identify patients with high risk of CINV. The CINV score is recalculated for each of patient's cycles and has no impact on patient's participation in the study and the randomized group.

The purpose of secondary analysis is to identify other, potentially predictive factors among the 9 additional ones.

A simple logistic regression model with the development of CINV over three cycles of chemotherapy will be conducted to identify a set of factors with the largest potential contribution to CINV and those with P-value ≤ 0.25 will be taken

into further consideration. Generalized estimating equations (GEE), which adjust for patient clustering by chemotherapy cycle, will be used to determine the final set of additional risk factors.

By using reclassification analysis NRI (Net Reclassification Improvement) we will redistribute the patients according to the new set of risk factors. Finally, the set of primary risk factors and the new set of risk factors will be compared, by presenting NRI_e and NRI_{ne} , the event- and non-event reclassification index.

These indices can be interpreted as a change in True Positive Rate and the negative of change of False Positive Rate, when using a new model and comparing it to the previously used one.

The calculation will be performed in SAS, the NRI analysis will be done using a macro developed for this purpose. The code can be found at [6].

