### Secondary objectives:

2. Evaluate acute (0 to 24 hours), delayed (>24 to 120 hours), and overall (0-120 hours) CINV indicators in each cycle of chemotherapy

Time 0 is defined as the start time of the chemotherapy administration on Day 1 of each of the three cycles. CINV indicators are nausea and vomiting, their intensity and frequency and Quality of Life in the acute, delayed and overall period.

3. Evaluate the predictive role of potential risk factors in the development of CINV over three cycles of chemotherapy

Potential risk factors for CINV are those thought to be increasing the risk of CINV in patients receiving MEC reported in section 3.3.3. Risk factors for CINV and in section 3.6.3.1 where the risk score algorithm calculation by using predictive factors for CINV is explained.

4. Evaluate the safety profile of the antiemetic drug over three cycles of chemotherapy

5. Explore the effect of CINV on daily activities and quality of life in patients receiving moderately-emetogenic chemotherapy over three cycles of chemotherapy

6. Evaluate resource utilization and health economic outcome

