Functional Living Index-Emesis (FLIE) questionnaire, a validated, nausea and vomiting specific, patient-reported outcome instrument. The frequency and intensity of acute and delayed nausea and vomiting will be measured via MAT. Rescue medication will be allowed at any time, during every cycle. The choice will be left at the discretion of the Investigators. The intake of rescue medications, either prescribed or non-prescribed, must be recorded in the Patient's diary and in the eCRF.

Patients may withdraw the study at any time at their own willing, without giving further details or justification.

The investigator may also exclude a subject from the study on the basis of his/her clinical judgment:

- General or specific changes in the patient's condition which make the patient ineligible for further assessments according to the inclusion/exclusion criteria
- Non-qualification to perform consecutive cycles (e.g., for toxicity)
- Failure to return for follow-up visits

The planned study enrolment time will be 12–18 months, with each patient making maximum of 5 visits in total.

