6.3. Health economic endpoints

Health economic endpoints will be evaluated during the study cycles:

- Number of days and daily doses of rescue medication administered for the treatment of CINV
- Number of re-hydration bags given for at least grade 2 vomiting (more details below)
- The number of days of unplanned hospitalisations related to CINV and department of hospitalization (type of ward)
- The number of outpatient physician visits and health care consultations due to CINV (e.g., general practitioner)
- The number of unplanned laboratory test including those at unplanned hospitalisations due to CINV
- Discontinuation of chemotherapy treatment due to CINV
- Delay of chemotherapy administration due to CINV
- Days of absence from work

The grade 2 vomiting is characterized in CTCAE version 5 as vomiting requiring intervention in the form of IV hydration. In this study, we will consider 2-5 vomiting episodes in 24 hours after chemotherapy administration as grade 2.

7. Definitions

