8.1.3. Per Protocol Set

A Per Protocol (PP) population will consist of all patients in the FAS population who complete the study fully compliant with the protocol and without any major deviation. Patients in the PP population will be analyzed according to the treatment they actually received. Efficacy analyses based on the PP population will be considered supportive.

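### The risk-factor analysis in SAP 9.8 is confined to Per Protocol completers, so patients who stop early, including any who stop because of CINV, are dropped with all their observed cycles

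*SAP*

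**What the plan says.** The protocol lists as a secondary objective: "Evaluate the predictive role of potential risk factors in the development of CINV over three cycles of chemotherapy". Protocol section 3.6.1 adds that the extra factors will serve to refine the predictive model at the end of the trial.

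SAP 9.8 sets out the analysis:

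- **Population.** "The analysis will be performed using the Per Protocol population". No other population is named. SAP 8.1.3 defines this set as "patients in the FAS population who complete the study fully compliant with the protocol and without any major deviation".
- **Screening.** "A simple logistic regression model with the development of CINV over three cycles of chemotherapy will be conducted", and "those with P-value ≤ 0.25 will be taken" forward.
- **Final selection.** GEE, described as adjusting for clustering within patient.
- **Comparison.** The old and new factor sets are compared by net reclassification improvement (NRI).

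Treatment arm is not among the 16 listed factors, and the GEE covariates are not written out. SAP 7.8 says in general terms that the secondary analysis will allow for correlation within a patient.

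Stopping early is foreseen. SAP 6.3 lists "Discontinuation of chemotherapy treatment due to CINV" as a health economic endpoint, and SAP 5.1 lets the investigator exclude patients who cannot continue their cycles, for example because of toxicity.

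**The concern.** The outcome of this analysis is CINV, and CINV is one of the recognised reasons for not completing. Restricting to completers therefore lets the outcome help decide who is analysed. A patient with severe CINV in cycle 1 who then stops contributes nothing, although cycle 1 was fully observed.

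The analysis is meant to sharpen a prediction tool applied before a cycle, when nobody knows who will complete three. Reclassification depends on absolute predicted risk, so an understated CINV rate matters even where odds ratios hold up.

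Two details of the model are also open: the unit of the outcome in the screening step, and the handling of arm.

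**Working it through.** **1. The plan's attrition figure.** Inputs from SAP 9.2: 410 randomised, response 71% v 60%, three cycles, correlation 0.5, missing 0%, 7.5% and 15%, two-sided 5%, 80% power.

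- Variance factor with independent pairwise missingness: f = [2.775 + 2 × 0.5 × (0.925 + 0.85 + 0.925 × 0.85)] / 2.775² = 5.336 / 7.701 = 0.693.
- Log odds ratio = ln(1.632) = 0.490.
- N = 2 × (1.960 + 0.842)² × [1/(0.71 × 0.29) + 1/(0.60 × 0.40)] × 0.693 / 0.490² ≈ 409, against 410 stated.
- Completers: 410 × 0.85 = 348.5, against 348 stated.

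Both figures reproduce.

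**2. What the Per Protocol restriction discards.**

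- Patients: 410 − 348 = 62 (15%). This is a minimum, because major deviations are removed as well.
- Observed cycles in all randomised patients: 410 × (1 + 0.925 + 0.85) = 1,138.
- Assuming monotone dropout, 30.75 patients leave after cycle 1 and 30.75 after cycle 2. Their observed cycles number 30.75 × 1 + 30.75 × 2 = 92, and 92 / 1,138 = 8%.

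**3. What that could do.** The documents give no rate of stopping for CINV, so these simulations rest on assumptions.

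*Stopping depends on CINV alone.* Assume a factor odds ratio of about 2, correlation 0.5, and about 14% non-completion, all of it after a CINV cycle. The cycle-level CINV rate among completers is 27% instead of 34%, and the share of patients with any CINV is 44% instead of 51%. The factor's odds ratio barely moves, from 1.97 to 1.96. If stopping is unrelated to CINV, the rate stays at 34%.

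*Stopping depends on CINV and on the factor.* Assume a true odds ratio of 1.93 and about 15–16% non-completion, only after a CINV cycle:

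| Stopping after a CINV cycle, with / without the factor | Per Protocol odds ratio | Full Analysis Set, observed cycles |
|---|---|---|
| 33% / 12% | 1.42 | 1.78 |
| 38% / 5% | 1.19 | 1.70 |

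A second simulation from a true odds ratio of 1.80, with 33% / 12%, gives 1.32 on Per Protocol and 1.66 on the Full Analysis Set.

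**4. The screening level, if the simple logistic model is fitted to cycle rows.** For a factor constant within patient, the design effect is 1 + (3 − 1) × 0.5 = 2. The true level is 2 × [1 − Φ(1.150 / √2)] = 0.416. With correlation 0.3 it is 0.363, and with 0.7 it is 0.458. Simulation with 348 patients gives about 0.42.

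For factors that vary between cycles, simulation gives about 0.25 if they are independent across cycles and about 0.35 if their own correlation is 0.5. If gender, weight, smoking, alcohol and other nausea history are taken as constant and unrelated to CINV, the expected number passing is 5 × 0.416 = 2.1 instead of 5 × 0.25 = 1.25. With one outcome per patient, the simulated level is 0.25–0.26.

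**5. Arm.** With the arm odds ratio near 1.63 from the planning rates, leaving arm out moves a baseline factor's odds ratio from 2.00 to 1.98.

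**The case against.** Several points on the other side stand.

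- **No demonstrated bias.** The 15% is a planning allowance for missing data, assumed missing completely at random or at random. It is tempting to infer that the patients lost are mostly those who stopped for CINV. Nothing in the documents supports that; the set merely includes any who did. Where stopping depends on CINV alone, the odds ratio hardly changes.
- **The screening level may be right as written.** A reader might conclude that the plan misstates its 0.25 level. SAP 9.8 can equally be read as one outcome per patient over three cycles, in which case 0.25 is correct, and SAP 7.8 promises allowance for correlation. Even on cycle rows, the screen only admits candidates and the clustered GEE step selects the final set.
- **Arm.** A reader might say that arm is left out of the model. The documents show only that adjustment for arm is not specified, and for baseline factors it scarcely matters.
- **No conflict with the protocol.** The Secondary analysis part of Protocol section 1 names no population and leaves the methods to the SAP. Choosing one there is not a deviation.
- **The remedy is partial.** Cycles after stopping stay unobserved in the Full Analysis Set too.

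None of this supplies a reason for making Per Protocol the only population. Elsewhere the SAP treats that set as supportive and the Full Analysis Set as the main basis for efficacy.

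**Conclusion.** The restriction is explicit, and a better choice is available at almost no cost. It discards at least 62 of 410 patients (15%) and, under monotone dropout, about 92 of 1,138 observed cycles (8%), by a criterion that the outcome can influence.

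The direction of risk is clear but its size is not. If stopping follows CINV, the CINV rate is understated. Factor odds ratios are at material risk only if stopping also depends on the factor, which is plausible for anxiety, fatigue or anticipatory symptoms but is an assumption.

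The figure of about 0.42 for the screen (0.36 to 0.46 for correlation 0.3 to 0.7) applies only to patient-constant factors in a model fitted to cycle rows. Its consequence would be extra candidates, not an invalid final step. The firm finding there is that the outcome's unit is undefined and that SAP 7.8 and 9.8 need to agree.

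Arm matters mainly for factors that treatment can change before cycles 2 and 3, such as CINV in the prior cycle.

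The point concerns one secondary objective and leaves the primary comparison untouched.

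**What to change.** In SAP 9.8:

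1. Run the risk-factor analysis on the Full Analysis Set using all observed cycles, and keep Per Protocol as a sensitivity analysis. State that this reduces the selection but does not fully remove bias from outcome-driven dropout.
2. Define development of CINV as a per-cycle outcome.
3. Use GEE with robust standard errors for the 0.25 screen as well as for the final model, so that 9.8 agrees with 7.8.
4. Include treatment arm in the association models, and state how arm is handled when NRI compares the new factor set with the existing score, which has no arm term.

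The change needs SAP wording and a little more analysis work. It needs no new data, since the cycles concerned are already to be collected.
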